To address *hypothesis 4*, a multiple linear regression with intervention condition (1=ORR+Project Brave; 0= ORR+waitlist control) and baseline parental distress in the context of child negative affect as predictor variables will indicate whether ORR+Project BRAVE versus ORR+delayed SSI led to greater reductions in parental distress from baseline to 2-week follow up. Parental distress will be indicated by the sum score of the distress tolerance scale. A p-value of $<.05$ will indicate a significant change in parental distress in the context of child negative affect from baseline to 2-week follow up.

Testing Assumptions

To justify the use of linear regression models for the purpose of prediction, we will check the following principle assumptions: 1) linearity and additivity of the relationship between dependent and independent variables, 2) statistical independence of the errors, 3) homoscedasticity of the errors, 4) normality of the error distribution. Nonlinearity will be tested by checking for a symmetric distribution of points on a plot of observed versus predictive values or residual versus predicted values. To check statistical independence of the errors, residual autocorrelations will be plotted to identify values that fall outside the 95% confidence band around zero. Homoscedasticity will be checked by plotting the residuals versus the predicted

values to examine the distribution of residual scores. Finally, normally distributed errors will be checked via normal probability plot to measure skewness and kurtosis.

Missing Data

We will impute any missing data using the expectation-maximization and bootstrapping algorithm implemented with Amelia II in R after running a sensitivity analysis to ensure that data is not missing at random. These imputed datasets allow for more conservative intent-to-treat analyses than listwise deletion or last-observation carried forward. We plan to impute as many datasets as there are percent of missing data for an outcome – rounding up to the next highest percentage (e.g., If 2.4% of data is missing on an outcome, we will create 3 imputed datasets). This process will allow us to retain high power even in the presence of missing data. Cohen's d effect sizes and 95% confidence intervals for analyses will be calculated using t -values for the treatment effects obtained from the analyses with the MOTE package in R.

False Discovery Rate

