The false discovery rate (FDR) will be applied to identify potential false-positive results. Q -values will be computed for p -values from each mixed effects linear model using an online calculator applying Benjamini and Hochberg's approach Benjamini and Hochberg's approach (1995); www.sdmproject.com/utilities/?show=FDR). Results from tests described above will be considered significant if FDR corrected $q < 0.05$.

Methodological Details Not Mentioned Elsewhere

Follow-up Period

We are intending on a 2 week follow-up period from the SSI but will allow up to 5 weeks post-intervention. Participants will be reminded once every two days for 6 days (total of 3 reminders) to complete the post-intervention questionnaires.

Operational Definition of Completion Rates for participants assigned to both conditions

Intervention completion rates for the ORR+ Project BRAVE group will be treated as a categorical (full completers, psychoeducational content completers, personalized-plan completers).

Categorical definitions of completion rates are defined as follows: full completers are all participants who reached the end of the SSI content (slide Q254), psychoeducational completers are all participants who received all of the psychoeducational content of the program (slide Q235), and personalized-plan completers are all participants who completed the step-by-step action plan for responding in a helpful way to their child's anxiety or avoidance (slide Q243)

Excluding Participants From Analysis

Participants will be excluded from analyses *only* if it is apparent from their free responses during the SSI that they are non-english speakers. If a participant completes either the baseline or

follow-up survey more than once, their *more-complete* response will be used in analysis (if responses are equally-complete, their *first* response will be used).

Differential Dropout Rates

We will assess for differential follow-up rates among full completers in each group by using Z-tests of differential proportions where we compare the proportion of people who drop out before completing the follow-up (Y or N) as a function of treatment condition (1 = ORR+Project Brave; 0 = waitlist control).

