For participants assigned to the ORR+ delayed SSI access group, a participant must have made it through all baseline measures (i.e., they must reach the final “page” of the baseline questionnaires, or the RCADS, though it is acceptable for the participant to leave the answer blank after seeing it) to be considered a “full completer”. For participants assigned to the ORR+Project BRAVE group, a participant must have made it through all of the intervention (i.e. they must reach the final “page” of the intervention) to be considered a full completer.

To be considered a follow-up “completer”, a participant must have made it through all of the questionnaires in the follow-up surveys (i.e. they must reach the final “page” of the follow-up questionnaires though it is acceptable for the participant to leave the answer blank after seeing it).

If the p value is greater than .05 we will assume dropout was not dependent on condition assignment and can proceed with interpreting the effects of intervention assignment. If the p value for this test is less than .05 we will conclude that dropout was dependent on condition assignment, and we will take the following steps to improve the interpretability of our results. Unequal dropout between treatment groups can introduce bias in trial results; however, this is not always the case (Bell, Kenward, Fairclough, & Horton, 2013; <https://doi.org/10.1136/bmj.e8668>). One major concern is that, if data is not missing at random, systematic differences may exist between “dropouts” and “completers” that cannot be corrected for, limiting the interpretability of our results. For example, if more control condition participants experienced a worsening of clinical symptoms and dropped out before completing follow-up measures, this worsening of symptoms would not be captured by completers’ data (or by data imputed based on the available completers’ data). Thus, should unequal dropout exist between conditions in the present study, we will report the results of our main analyses while highlighting (1) limitations to interpretation, and (2) ways in which this will inform future intervention development.

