Further, if unequal dropout is present, we will run a sensitivity analysis to determine a range of possible effect sizes for our outcomes of interest, varying how much “dropout participants” may have changed on each outcome. To establish lower- and upper-end estimates of effect size, we will: (1) calculate residual change for each of our 3 outcomes, (2) identify the 25th and 75th percentile values for residual change in each outcome, (3) run analyses for each outcome where we impute the lower residual change value (25th percentile) for all dropouts/missing data, as well as the higher residual change value (75th percentile) for all dropouts/missing data. This approach explicitly assumes data are not missing at random, providing a more unbiased estimate of the overall treatment effect in the presence of unequal dropout.

Exploratory Moderation Tests

We will also conduct exploratory moderation tests examining various baseline variables as moderators of the SSI's impact on outcome, using the same approaches to missing data and corrections for multiple tests as described elsewhere in the pre-registration

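### The SAP gives BRAVE parents' progress through the session no stated role in the imputation, and its dropout safeguard does not count those who left early; naming progress as an imputation variable is a cheap improvement

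*SAP*

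**What the plan says.** All references are to the SAP.

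- **Who is analysed.** Under Excluding Participants From Analysis, the only ground for exclusion is being evidently a non-English speaker. A BRAVE parent who leaves the SSI early therefore stays in the intent-to-treat set, and a missing follow-up has to be imputed.
- **Imputation.** Missing Data states: "We will impute any missing data using the expectation-maximization and bootstrapping algorithm implemented with Amelia II in R". It names no imputation variables. The analysis regressions for hypotheses 1 and 4 contain condition and the baseline score only.
- **SSI progress.** Under Operational Definition of Completion Rates: "Intervention completion rates for the ORR+ Project BRAVE group will be treated as a categorical". The categories are tied to slides Q235 (psychoeducation), Q243 (action plan) and Q254 (end).
- **Dropout test.** Under Differential Dropout Rates: "We will assess for differential follow-up rates among full completers in each group". A full completer in BRAVE must have reached the last page of the intervention; in the control arm, the last baseline page.
- **Sensitivity analysis.** In the same section: "if unequal dropout is present, we will run a sensitivity analysis to determine a range of possible effect sizes". It assigns the 25th, then the 75th, percentile of residual change to everyone with missing data. Missing Data also mentions a check before imputation, "after running a sensitivity analysis to ensure that data is not missing at random", but does not describe it. As worded, it is the reverse of the missing-at-random condition on which standard Amelia imputation relies.

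**The concern.** In BRAVE, the share of the intervention received differs between parents, and the SAP's own definitions require it to be recorded, including for parents later lost. Parents who leave early may gain less and may also be less likely to answer at two weeks. If both hold, missingness within BRAVE is related to outcome even after conditioning on arm and baseline. An imputation that ignores progress then fills early leavers' gaps mainly from parents who finished.

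The safeguard does not catch this. Early leavers are outside the dropout test, so heavy loss among them cannot make it significant. With p above .05, the SAP proceeds to interpret the effects without the percentile analysis. At stake are the intent-to-treat estimates for hypothesis 1 (the primary outcome) and hypothesis 4.

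**Working it through.** The SAP states no figure on this point to reproduce. Every rate below is an assumption; only the 150 per arm comes from the SAP.

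**Closed form.** Let L be the share of BRAVE parents who leave early, ml and mf the follow-up loss in leavers and finishers, and k the leavers' effect as a fraction of the finishers' effect. Imputing on arm and baseline alone returns the observed-case effect in BRAVE. The ratio of imputed to true all-assigned effect is

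R = {[(1−L)(1−mf) + kL(1−ml)] / [(1−L)(1−mf) + L(1−ml)]} / [(1−L) + kL].

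*Worked example:* L = .30, ml = .70, mf = .15, k = 0.
- (1−L)(1−mf) = .70 × .85 = .595
- L(1−ml) = .30 × .30 = .09
- .595 / .685 = .869, and .869 / .70 = 1.24

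*Range:* L from .20 to .40, ml from .50 to .80, mf from .10 to .20.

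| k | Mildest case (L .20, ml .50, mf .20) | Most severe case (L .40, ml .80, mf .10) |
|---|---|---|
| 0 | (.64/.74)/.80 = 1.08 | (.54/.62)/.60 = 1.45 |
| 0.5 | (.69/.74)/.90 = 1.04 | (.58/.62)/.80 = 1.17 |

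*No-bias cases:* with k = 1, both parts of R equal 1. With ml = mf, the follow-up rate cancels and again R = 1.

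**Simulation of the worked example.** Inputs: N = 300, baseline correlation .6 (residual SD .8), and an effect of .40 residual SD in finishers and none in leavers. The true effect is .40 × .80 × .70 = 0.224 outcome units.

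| Imputation model | Estimated reduction (two separate runs) | Coverage of 95% interval | Standard error |
|---|---|---|---|
| Arm and baseline | 0.276; 0.288 | .92; .90 | 0.107 |
| Arm, baseline and progress | 0.222; 0.232 | .95; .95 | 0.116 |

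The closed form predicts .869 × .32 = 0.278 for the first row. When leavers were given the same benefit as finishers, neither model was biased.

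**A second set of assumptions.** 70% finish, finisher effect 0.30, follow-up 80% in finishers and 75% in controls, no effect in leavers (true effect 0.21).
- Leavers followed up at 30%: 0.26 without progress, 0.21 with it.
- Leavers followed up at 10%: 0.29 without progress, 0.20 with it.

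**How finely progress can be split.** With 150 in BRAVE, L = .30 and ml = .70, there are 45 leavers and 13 or 14 of them observed, about 4 or 5 for each of the three non-finishing levels (none, Q235, Q243). With L = .20 and ml = .80, 30 leavers yield 6 observed, or 2 per level. Only the two-way split, reached Q254 or not, is dependable in advance.

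**The case against.** Several stronger readings are tempting, and the SAP does not support them.

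- *A reader might infer that the SAP excludes SSI progress from the imputation.* It lists no imputation variables at all, so progress is unassigned rather than ruled out. An arm-and-baseline model is itself an assumption. If arm were also left out, which the wording allows, the second set of assumptions gives 0.18 against a true 0.21 (leavers followed up at 30%), an understatement. The document does not fix even the direction.
- *A reader might infer that early leavers are simply given finishers' outcomes*, from the phrase "or by data imputed based on the available completers’ data". Completers there are follow-up completers: "To be considered a follow-up “completer”, a participant must have made it through all of the questionnaires in the follow-up surveys". Nothing bars an early leaver from follow-up, and those who answer contribute their own outcomes. The formula above allows for this.
- *A reader might infer that the milestones are used nowhere.* Reaching the end of the SSI defines the population of the dropout test.
- *A reader might infer that the BRAVE effect is overstated.* That needs both lower benefit and lower follow-up in early leavers, and the SAP gives no figures for either. Its own example, control parents who worsen and drop out, would work in the opposite direction.

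The shift is also modest: (0.276 − 0.224) / 0.107 is about half a standard error in the example. And where almost no early leavers answer, adding progress leaves almost nothing to impute from.

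All of this stands as a limit on the claim. It does not remove the gap: a variable that the SAP already defines, and that could plausibly explain missingness, has no stated role in the imputation, and the trigger for the fallback analysis leaves out the parents concerned.

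**Conclusion.** The point holds as a cheap improvement to the plan, not as a demonstrated bias. The SAP leaves the imputation model unspecified, gives SSI progress no role in it, and triggers its percentile sensitivity analysis by a test that does not count BRAVE early leavers. If that analysis is triggered, it does reach all missing data, but with one common value and no stated split by arm or progress.

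Conditional on early leavers benefiting less and being lost more often, and on an imputation using arm and baseline, the overstatement is 8% to 45% when leavers gain nothing and 4% to 17% when they gain half, over the ranges assumed. It is zero under equal benefit or equal follow-up. Adding progress removed the bias in simulation within simulation error.

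**What to change.** In Missing Data, state that the Amelia II model includes:

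1. arm and the baseline scores;
2. SSI progress in the BRAVE arm, coded as reached Q254 or not (for example, an indicator set to zero for controls), with the finer milestones only if enough non-finishers answer follow-up;
3. the immediate post-session change rating where available. It will often be absent in early leavers.

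Leave the analysis regression as condition plus baseline. If almost no early leavers answer follow-up, the imputation cannot be rescued this way; in that case base the sensitivity analysis under Differential Dropout Rates on all randomised parents, not on full completers. The wording of the check that precedes imputation should be corrected at the same time.

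The cost is SAP text and variables that the SAP already defines. The standard error rises slightly (0.107 to 0.116 in the example), because uncertainty about early leavers is then carried into the estimate.

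### The SAP states the missing-data assumption behind its imputation backwards, and runs its only not-missing-at-random analysis only when dropout differs significantly between arms

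*SAP*

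**What the plan says.** In the SAP's Missing Data section: "We will impute any missing data using the expectation-maximization and bootstrapping algorithm implemented with Amelia II in R", and this happens "after running a sensitivity analysis to ensure that data is not missing at random". No procedure for that check is named, and nothing is said about what follows from its result. The imputed data carry the main analyses: "These imputed datasets allow for more conservative intent-to-treat analyses than listwise deletion or last-observation carried forward". The number of imputations follows the percentage missing ("If 2.4% of data is missing on an outcome, we will create 3 imputed datasets").

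The Differential Dropout Rates section uses the same term as a warning: "if data is not missing at random, systematic differences may exist between" dropouts and completers, of a kind that cannot be corrected for. Its example is control participants who get worse and leave. Their worsening would not be seen in completers' data, "or by data imputed based on the available" completers' data.

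The same section then gives a separate analysis, which fills in the 25th and then the 75th percentile of residual change for dropouts. Of it the SAP says "This approach explicitly assumes data are not missing at random". It has a trigger: "if unequal dropout is present, we will run a sensitivity analysis to determine a range of possible effect sizes". Unequal dropout means p below .05 on a Z-test comparing dropout proportions between conditions.

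**The concern.** Amelia II draws missing values from a model fitted to the observed data. That is justified when data are missing at random (MAR) given the variables in the model. The Missing Data section names the opposite state as the thing to be ensured beforehand, and it is the SAP's only statement of the assumption behind the imputed intent-to-treat analyses.

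Two things are at stake. First, a pre-registered plan should say what its main result assumes. Here a reader cannot tell whether the authors meant MAR, a test against missing completely at random, or an analysis of the percentile type. Second, the protection against a wrong MAR assumption depends on a significance test of dropout rates. If that test is not significant, the SAP says dropout will be taken as independent of condition and the effects interpreted, with the reversed sentence as the only remaining mention of the problem.

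**Working it through.** No figure in the SAP has to be reproduced for this point. The imputation-count example is consistent (2.4% rounds up to 3).

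**1. Direction.** Side by side:

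- Missing Data: impute with Amelia II, having ensured that data are *not* missing at random.
- Differential Dropout Rates: if data are not missing at random, imputation from completers does not capture worsening among dropouts.
- Same section, later: the method offered for that state is percentile imputation, not Amelia II.

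The first statement ties the method to the state in which the second says it fails.

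**2. Testability.** Whether missingness depends on unseen scores, given the seen ones, cannot be learned from the seen ones. Observed data can at most speak against missing completely at random. A sensitivity analysis explores departures from an assumption; it cannot ensure one. Replacing the clause with a promise to ensure that data *are* missing at random would therefore leave this fault in place.

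**3. The trigger.** The Z-test compares how many drop out in each arm. MAR concerns which participants drop out. Equal numbers can leave for different reasons, so p > .05 says nothing about MAR.

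**4. Size of the general risk (assumed inputs).** The SAP gives no dropout rate. Let m be the fraction of controls missing and delta the amount, in SD, by which their true scores are worse than imputed, with BRAVE dropouts as imputed. Then bias in the group difference ≈ m × delta:

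| m | delta | bias (SD) |
|---|---|---|
| 0.20 | 0.3 | 0.06 |
| 0.20 | 0.5 | 0.10 |
| 0.30 | 0.3 | 0.09 |
| 0.30 | 0.5 | 0.15 |

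**5. Simulation (assumed inputs).** It used 300 participants, 150 per arm (the SAP's target), a true effect of −0.30, baseline slope 0.6 and residual SD 0.8 (total variance 0.36 + 0.64 = 1, before the treatment effect). Bootstrap-based normal imputation was run with 20 imputations and Rubin's rules, over 1,500 replicates. This follows the principle of Amelia II but is not the package itself.

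| Dropout depends on | Missing | Mean estimate | Bias | 95% CI coverage |
|---|---|---|---|---|
| baseline (MAR) | 29.5% | −0.298 | 0.002 | 94.5% |
| unseen outcome, same way in both arms | 27.1% | −0.276 | 0.024 | 94.1% |
| unseen outcome, controls only | 28.6% | −0.136 | 0.164 | 68.1% |

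The third row is the SAP's own example. About half the effect is lost (0.164 / 0.30 = 55%).

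**6. What the percentile analysis shows when dropout is equal.** Let r_T and r_C be completers' mean residual change, m_T and m_C the missing fractions, and q the single value filled in for all dropouts. The group difference is about (1 − m_T)r_T − (1 − m_C)r_C + q(m_T − m_C). If m_T = m_C the last term is zero, so the 25th and 75th percentile runs give the same answer. This bears on the fix.

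**The case against.** The strongest reply is that the sentence changes no analysis. The SAP says any missing data will be imputed; it writes no threshold, no if/else rule and no alternative. A reader might infer that imputation goes ahead only once data have been shown not to be missing at random, but the text does not go that far. Delete the clause and the imputed datasets, regression and p-values are the same. This stands.

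It follows that the figures of 0.06 to 0.15 SD cannot be charged to the wording. A reader might take them as the harm done by the sentence. They are the bias of any MAR imputation when one arm departs from MAR, and would be the same after rewording. This also stands.

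Nor does data not missing at random always mean a badly biased contrast: with the same dropout mechanism in both arms, the simulated bias was small (0.024).

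The authors also plainly know that data not missing at random are a problem, so a slip is the likelier reading. If missing completely at random was meant, observed data could at least speak against it. That is fair, but the SAP does not show which meaning was intended, and it uses the term in its technical sense in the later section.

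Finally, a reader might conclude that the plan has no analysis for data not missing at random. It has one. The gap is its trigger.

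**Conclusion.** The point holds as an error of stated assumption together with a badly placed trigger. The clause is reversed, conflicts with the SAP's own reasoning on dropout, and promises something that observed data cannot deliver. The one analysis that would inform readers about departures from MAR is withheld whenever the Z-test is not significant, which is no evidence for MAR.

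The documents do not support saying that the main analysis is biased because of this sentence, or that imputation is formally gated on it. The size given (0.06 to 0.15 SD) rests on assumed dropout of 20–30% and a one-arm shift of 0.3–0.5 SD, neither of which is in the SAP. It shows why the sensitivity analysis should be unconditional. The direction depends on who leaves: in the SAP's example benefit is hidden, while other patterns could inflate it.

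**What to change.** 1. In Missing Data, delete the clause about ensuring that data are not missing at random.
2. In its place, state that imputation assumes outcomes are missing at random given condition, baseline scores and the other variables in the imputation model; list those variables; and say that the assumption cannot be tested from the trial's data.
3. In Differential Dropout Rates, remove the condition on the percentile analysis, so that it is always run and reported beside the main result, whatever the Z-test shows. The Z-test can stay as a description.
4. So that this analysis is informative when dropout is about equal (step 6 of the working), include runs in which the two arms receive different percentiles: the 25th in one and the 75th in the other, and the reverse.

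The cost is a few sentences in the SAP, a few extra runs per outcome and a little more reporting. The imputation code does not change.

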Using G*Power 3.1, sample sizes needed to detect group differences in the primary outcome (changes in accommodation from baseline to follow-up) between the BRAVE group and the Control group of small (.2), medium (.5), and large effects (.8) based on an F test, linear multiple

regression with $\alpha = .05$ and power = 0.80 were 395, 55, and 25, respectively for the primary outcome (hypothesis 1). The target sample of 300 (150 per SSI condition accounting for attrition) reflects power to detect a small to medium effect as observed by previous SSI trials.

Analytic Plan

To address *hypothesis 1*, a multiple linear regression with intervention condition (1=ORR+Project Brave; 0=ORR+waitlist control) and baseline accommodation levels (sum score of the first 9 items of the Family accommodation scale with higher scores indicating higher levels of accommodation) as predictor variables will indicate whether ORR+Project BRAVE, versus ORR+delayed SSI access, led to differential reductions in accommodation behavior from baseline to 2-week follow up. A p-value of $<.05$ will indicate a significant change in parental accommodation from baseline to 2-week follow up.

To address *hypothesis 2*, we will use the two-sample t-test to determine whether the difference between the ORR+project BRAVE and ORR+delayed SSI access group's mean ratings of the perceived post intervention condition change item is significant. A p-value of $<.05$ will indicate a significant difference between the two conditions. Descriptive statistics of the scores for both conditions will be reported as well with a mean rating above 3 (out of 5) indicating an overall, subjectively-detectable pre-to-post change.

To address *hypothesis 3*, we will examine mean scores on the Program Feedback Scale from the intervention group only. A score above 3 on any given program feedback scale item will reflect endorsement of that item (e.g. positive feedback/adequate acceptability). Thus, a mean score of 3 or higher (out of 5) across participants in this study will indicate participants found the intervention acceptable.

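### For hypotheses 1 and 4, Cohen's d is taken from a baseline-adjusted t-value, so it is scaled by the residual SD and is not the conventional d its label implies

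*SAP*

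**What the plan says.** The rule for effect sizes closes the Missing Data section of the SAP: Cohen's d and its 95% confidence interval "will be calculated using t -values for the treatment effects obtained from the analyses", using the MOTE package in R. No standardising SD is named, no conversion formula is given, and nothing says that the resulting d is on a residual scale.

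The analyses that supply the t-values are set out in the Analytic Plan:

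- Hypothesis 1: "a multiple linear regression with intervention condition (1=ORR+Project Brave; 0=ORR+waitlist control) and baseline accommodation levels" as predictors.
- Hypothesis 4: condition and "baseline parental distress in the context of child negative affect as predictor variables".
- Hypothesis 2: no covariate; "we will use the two-sample t-test to determine whether the difference" between the group means is significant.

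Missing data are multiply imputed with Amelia II: "We plan to impute as many datasets as there are percent of missing data for an outcome", rounded up. The SAP does not say how estimates or t-values are combined over the imputed datasets.

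If dropout is unequal, the Differential Dropout Rates section adds a sensitivity analysis that reports a range of effect sizes. In it, every dropout is given a single residual-change value, first the 25th and then the 75th percentile.

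**The concern.** In a two-sample t-test with complete data, t and the group sizes are enough to recover the mean difference over the pooled SD. Once the baseline score is a covariate, they are not. The standard error of the condition coefficient is then built on the SD left after baseline has been removed, and t alone carries no trace of the raw SD. A d computed from that t depends on how well baseline predicts follow-up as well as on the size of the intervention effect. If the t is pooled over imputations, it depends on the amount of missing information too.

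At stake is the reading of the effect estimate. This d with its interval is the only standardised effect measure that the SAP names for the treatment comparisons. Two trials with the same difference in scale points and the same raw SD could report different values under the same label. A reader who takes the figure as conventional d would misjudge the size of the effect, in a direction that cannot be known in advance.

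**Working it through.** **The plan's own figures.** The SAP states no d for any outcome, so there is none to reproduce. Its nearest figures are total sample sizes of 395, 55 and 25 for effects described as "small (.2), medium (.5), and large effects (.8"). With a noncentral F test of one predictor (alpha .05, power .80), these reproduce exactly at f² = .02, .15 and .35. They do not follow from .2, .5 and .8 read as Cohen's d, which give 786, 126 and 50 in total (normal approximation). This bears on the objection below; the mislabelling itself is a separate matter.

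**Inputs.**

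- From the SAP: 150 per arm; baseline-adjusted regression for hypotheses 1 and 4; unadjusted t-test for hypothesis 2; multiple imputation, with the number of datasets equal to the percentage missing.
- Assumed, because the SAP does not give them: r, FMI, the conversion d = t × sqrt(1/n1 + 1/n2), and pooling by Rubin's rules.

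**Step 1, complete data.** In the adjusted regression, t ≈ b / [s_res × sqrt(1/n1 + 1/n2)], where b is the adjusted difference and s_res the residual SD. Multiplying by sqrt(1/n1 + 1/n2) gives b / s_res. With equal variances at both times, s_res = SD × sqrt(1-r²), so the t-based d equals (b/SD) / sqrt(1-r²).

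**Step 2, imputation.** Under Rubin's rules the pooled variance includes a between-imputation part. This enlarges the standard error and multiplies the t-based d by about sqrt(1-FMI). The net factor is sqrt((1-FMI)/(1-r²)).

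| r | factor, FMI = 0 | d of .30 becomes | factor, FMI = .3 | d of .30 becomes |
|---|---|---|---|---|
| .4 | 1/sqrt(.84) = 1.09 | .33 | sqrt(.7/.84) = 0.91 | .27 |
| .5 | 1/sqrt(.75) = 1.15 | .35 | sqrt(.7/.75) = 0.97 | .29 |
| .6 | 1/sqrt(.64) = 1.25 | .38 | sqrt(.7/.64) = 1.05 | .31 |
| .7 | 1/sqrt(.51) = 1.40 | .42 | sqrt(.7/.51) = 1.17 | .35 |

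Over r from 0 to .8 and FMI from 0 to .4, the factor runs from 0.77 (r = 0, FMI = .4) to 1.67 (r = .8, FMI = 0). It is 1 where FMI = r², for example r = .5 and FMI = .25.

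**Step 3, simulation.** There were 400 trials per cell with 150 per arm, a true raw d of .30, normal-model imputation and Rubin pooling. At 0, 20 and 30% missing, the t-based d averaged .34, .31 and .29 for r = .5, and .42, .38 and .36 for r = .7. Dividing the adjusted difference by the raw pooled SD gave .29 to .31 in every cell.

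**Step 4, the dropout sensitivity analysis.** Giving all dropouts one constant residual-change value removes residual variation. If the t-based rule is used there too, with assumed dropout of 20% and 35% in the two arms, the ratio of t-based d to the adjusted difference over the baseline SD is about 1.27 at r = .5 and 1.54 at r = .7 in simulation. The complete-data ratios are 1.15 and 1.40. The range would therefore be on a different scale from the main estimate.

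**Hypothesis 2.** There is no covariate, so with complete data the t-based d is the ordinary d. Only the sqrt(1-FMI) term can affect it.

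**The case against.** The strongest reply is that residual standardisation is a legitimate, definable metric and is consistent with the plan's own power calculation. The sample sizes come from f², which is itself residual-scaled: for one tested predictor in two equal groups, d = 2f, so f² = .02 corresponds to 2 × sqrt(.02) = .28 residual SDs. A t-based d is on that scale and a raw-SD d is not. This stands as a reason why labelling the figure would be acceptable. It does not rescue an unlabelled Cohen's d, because the plan presents its benchmarks as .2, .5 and .8, which are the familiar values for conventional d.

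It can also be said that the conclusions rest on p-values and FDR-corrected q-values, which the choice of standardiser does not alter. That is true, and it limits the consequence to reporting and interpretation.

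Three stronger readings are tempting, and the document does not support them.

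- **The plan exaggerates the effect.** Residual scaling enlarges d and pooled imputation error shrinks it. At FMI = .3 the net factor is below 1 for r = .4 and .5, and the SAP gives neither r nor an attrition rate.
- **The d will be misread against earlier single-session trials.** The Sample Size Justification mentions such trials without a figure or a standardiser, so whether comparability is lost cannot be judged. Nor does the SAP say that results will be graded against .2, .5 and .8.
- **Hypothesis 2 has the same fault.** It does not, except through imputation.

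**Conclusion.** The point holds for hypotheses 1 and 4. Following the plan as written yields a d in residual-SD units under a label that readers will take to mean raw-SD units. With complete data the factor is 1.09 to 1.40 for r between .4 and .7. With imputation it may lie on either side of 1.

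The parts differ in certainty. That the t from a baseline-adjusted model carries the residual SD follows directly from the text and simple algebra. The exact conversion is assumed, since the SAP names a package but no formula. The imputation term is inferred, since no pooling rule is stated. The numerical sizes rest on assumed r and FMI. Near-cancellation at values such as r = .5 and FMI = .25 would be coincidence and is no safeguard.

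This should be corrected before results are seen, but it does not threaten the validity of the hypothesis tests.

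**What to change.** Replace the effect-size sentence in the Missing Data section with a rule that does the following:

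- For hypotheses 1 and 4, report the adjusted mean difference and its 95% confidence interval, pooled over the imputed datasets by a stated rule.
- Obtain d and its interval by dividing both by a named raw SD, for example the pooled baseline SD of that scale. State that the interval treats this SD as fixed.
- Use the same standardiser in the sensitivity analyses under Differential Dropout Rates, so that the range and the main estimate share one scale.
- For hypothesis 2, the mean difference over the pooled SD of the rating keeps d free of the imputation term.

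If the t-based figure is kept, label it as standardised by the residual SD.

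The cost is a sentence or two in the SAP and a few lines of code. The reported d may turn out larger or smaller than the t-based one, which is a reason to settle the choice now.
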